7.4. Time Periods

Each patient will have an index date corresponding to the date of their first prescription for *Duavee* or E+P HRT treatment after 01 May 2014. Baseline characteristics will be assessed from patient data collected prior to their index date (baseline period). A baseline period will be specified in a manner that balances inclusion of as many *Duavee* users as is feasible in the cohort with the need to ascertain covariates prior to the start of treatment. The baseline period will be determined prior to conducting analyses based on review of the distribution of prior continuous health plan enrolment among the *Duavee* cohort of patients.

As described in [Section 7.1](#), follow-up will continue from the first use of *Duavee* or E+P HRT through to the earliest occurrence of a censoring event.

[figure not shown]
Patients will accrue both person-time at risk and person-time on treatment. Analyses will consider patients at risk during the entirety of their follow-up until censoring, regardless of treatment discontinuation. Exploratory analysis will be done on the timing of events in relation to being on treatment.

Scenarios illustrating the duration of the follow-up period are presented in Figure 3.

[figure not shown]
Figure 3. Safety endpoints

- Key:**
- Enrolled in a health plan
 - Exposure to *Duavee*
 - ▨ Exposure to comparator E+P HRT

Patient A: *Duavee* cohort member censored due to use of a comparator E+P HRT

Patient B: E+P HRT cohort member censored due to end of health plan enrolment, history of MI diagnosed at baseline.

Data Source

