Study design: This PASS is a retrospective cohort study utilizing a US healthcare claims data source (HealthCore Integrated Research DatabaseSM [HIRD]). Two treatment groups of new initiators (*Duavee* and E+P HRT) will be defined and followed for each specified endpoint until the end of the study period or until that endpoint occurs. Other censoring events include hysterectomy, switch of index treatment, and disenrollment from the HIRD, diagnosis of cancer or death. The planned study will be 4 years in duration and will follow new initiators identified in 2014-2018.

Study Population: All patients identified in the HIRD who have received at least one prescription for *Duavee* or E+P HRT since May 2014 (US commercial launch date), and have a baseline period (e.g., 6 or 12 months to be determined by a priori analyses) prior to their first study medicine prescription, will be included in this study. Patients without a uterus and those with an existing cancer diagnosis will be excluded. Only new initiators will be included in the main analysis. To be a new initiator, patients need to have no recorded use of either *Duavee* or E+P HRT products in their baseline period. Patients with prior use of E+P HRT in either the *Duavee* or E+P HRT cohort will be excluded from the main analyses, but will be included in sub analyses. Similarly, patients with a history of unopposed estrogen use in their baseline period will be analyzed in sub analyses but excluded from the main analyses. Figure 4 in [Section 7.7](#) details the analysis populations.

Variables: Variables will be defined and analyzed that represent patient characteristics, comorbidities, utilized medications, medical history, and safety endpoints. A listing of study variables is provided in [Section 7.3.1](#).

Data source: The HIRD is a longitudinally integrated, US research database comprising payment claims for healthcare encounters among included health insurance plans. It is among the largest of its kind in the US and has been extensively used for pharmacoepidemiologic research, including many PASS.^{1,2,3,4}

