5. RATIONALE AND BACKGROUND

In the EU, CE/BZA (authorized as *Duavive* 0.45 mg/20 mg modified-release tablets) is indicated for the treatment of estrogen deficiency symptoms in postmenopausal women with a uterus (with at least 12 months since the last menses) for whom treatment with progestin-containing therapy is not appropriate.

In the US, CE/BZA (authorized as *Duavee*) is indicated for use in women with a uterus for the treatment of moderate to severe VMS associated with menopause; and for the prevention of postmenopausal osteoporosis. *Duavee* has been commercially available in the US since May 2014, and is planned to be made commercially available in the EU during 2015. Compared to the EU, the US indication for *Duavee* is broader (i.e., not restricted to those whom progestin-containing treatment is inappropriate, and indicated for osteoporosis prevention). Therefore, it is anticipated that by conducting the PASS in the US, the population of women who would be indicated for *Duavive* in the EU will also be adequately

represented. This study will collect real-world data on the risks of various endpoints among populations for which the product is prescribed. Because *Duavee* is an estrogen-containing product, endometrial hyperplasia and endometrial cancer are relevant safety events and have been designated as primary safety endpoints, while all other safety events are secondary endpoints.

This PASS is designed to provide interim reports at regularly scheduled intervals over the duration of the study. The rationale for conducting the study in a US population is to draw from the broader patient population indicated for *Duavee*, as well as to achieve large study samples sooner than would be possible if the study were to rely on data obtained from the EU. These advantages are based on the earlier launch of the product in the US as compared to the EU, and the large size is due to the greater sample sizes accessible in US healthcare data sources.

This protocol describes a NIS designated as a PASS that will be conducted in the US as a post-authorization commitment to the EMA.

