7. RESEARCH METHODS

7.1. Study Design

This PASS is a retrospective cohort study utilizing a healthcare claims data source (HIRD) in the US. Two (2) treatment groups (*Duavee* and E+P HRT) will be identified, followed, and reported upon using annual database updates. A new-user cohort design will be used for the main analysis and users with a history of (E+ P) HRT will be examined in sub-analyses. The study will accumulate data for 4 years (May, 2014-May, 2018) as it follows a dynamic cohort of patients that enter the study at different times, based on when *Duavee* or E+P HRT is initiated.

Figure 1 shows the length of study follow-up according to when new users enter the cohort.

The study duration was determined based on sample size calculations, and is the soonest that clinically meaningful HRs for endometrial hyperplasia and endometrial cancer can be detected. Study years and reporting intervals will run from May 1 through April 30 of the next year. Interim (follow-up) and final reports will contain both interval and cumulative data.

All patients in the HIRD who initiate *Duavee* or E+P HRT in the study period (2014-2018) will be considered for inclusion. This PASS is a retrospective cohort study using secondary data. The source data has been accruing since *Duavee* became available in the US in May, 2014. In accordance with EMA Pharmacovigilance Guidance (Module VIII)⁵, the start of a PASS using secondary data is defined to be when the analytic dataset is extracted. This will not be done for this PASS until the study protocol has been approved by the PRAC.

Follow-up will continue from the first use of *Duavee* or E+P HRT through to the earliest of the following censoring events:

- End of continuous health plan eligibility;
- Switch from *Duavee* to an E+P HRT medication or vice-versa;
- (Note: Any use of an estrogen or estrogen-containing product (Appendix 2) that differs from the HRT treatment regimen dispensed on the index date will censor follow-up. This does not include dispensing of a topical estrogen that is a single-unit

E+P HRT. As described in [Section 7.7.4](#), sensitivity analyses exploring the impact of this criterion will be performed.

- First occurrence of a safety endpoint.

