7.2.1. Inclusion Criteria

All patients identified in the HIRD who have received a prescription for *Duavee* or E+P HRT since May 2014 (date of first commercial availability in the US), and have a baseline period (e.g., 6 or 12 months to be determined by a priori analyses) prior to their first study medicine prescription, will be included in this study. Codes for *Duavee* and specific E+P HRT products are listed in Appendix 2.

- To be included in the main analyses, patients need to be new initiators of *Duavee* or E+P HRT as evidenced by a sufficient baseline period (e.g., 6 or 12 months to be determined using a priori analyses) prior to their first study drug prescription with no prior use of either *Duavee* or E+P HRT.
- The duration of the baseline period will be determined prior to the start of the analysis. The analysis will assess the distribution of continuous enrollment prior to the first dispensing of *Duavee* among the exposed patients. Selection of a threshold will balance inclusion of as many *Duavee* users as is feasible with the need to ensure appropriate capture of baseline covariates among the included patients.
- Sub-analyses will be performed for those with either (1) use of E+P HRT (i.e., not new initiators), or (2) unopposed estrogen in their baseline period. See Figure 4 in Section [Section 7.8](#) for the flow of patients to the separate analyses.

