7.7.2. Sub Analyses

Women with a previous history of E+P HRT use, different from their index drug (i.e., *Duavee* or specific E+P HRT) require special analytic considerations. In a new-user cohort design (as in the main analysis), these types of patients are excluded for several reasons. First, if women with past use of HRT incur a study endpoint, it is difficult to determine whether the endpoint is due to previous HRT or current HRT use. Further, women for whom previous HRT use was associated with poor outcomes (e.g., adverse effects) are likely to be under represented among those initiating *Duavee* or E+P HRT, which would deplete susceptible women and result in a survivorship bias or could lead to channeling of these

patients to one study drug over the other. Finally, baseline factors of women with previous use of HRT (e.g., comorbidities) could include effects of HRT (e.g., uterine bleeding) that could be intermediate in the causal pathway between exposure and study endpoints (e.g., endometrial hyperplasia, endometrial cancer). Controlling for factors that are intermediate in the causal pathway under study is to be avoided as it can invalidate a given analysis. Because of these limitations, analyses of the primary and secondary endpoints among *Duavee* and E+P HRT exposed patients with a previous history of HRT use will be limited to estimation of IRs and their associated 95% CI for each cohort overall and stratified IRs by the variables listed in the main analyses (patient age, treatment duration, time since last exposure, and exposure to local hormone therapy). These stratified analyses will only be done once there are at least 4 events in both the *Duavee* and E+P HRT groups.

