- Use of administrative healthcare data for research is associated with outcome misclassification, due to missing codes or coding errors, or to limits in the time period of patient observation available in the data. This study will use well-established sources, but misclassification may still be present. Specifically, women who have had a hysterectomy before their baseline 12 month period and started either *Duavee* or E+P HRT would be misclassified as having an intact uterus. However, this misclassification would be non-differential and would not bias the study comparison.
- There may be uncontrolled residual confounding aspects due to unmeasured prescribing factors that differ between the *Duavee* and E+P HRT patient cohorts. Physicians prescribe drugs for specific medical reasons and this may introduce channeling biases whereby one cohort is at higher risk for a particular safety event. This bias could also be due to unrecorded cardiovascular and cancer risk factors such as smoking, body mass index (BMI), and family history. Because the analyses rely on automated claims collected primarily for billing purposes, some desirable data elements are not captured. Lifestyle factors such as smoking and biometric measures like BMI, for example, are systematically unavailable. Likewise, family history of endpoints is unknown. These factors present another source of residual confounding.
- Despite the large size of the HIRD, the identified safety endpoints are rare events so there will be a limit to the precision with which it can estimate elevated risks associated with *Duavee* use. Additionally, the cancer endpoints may have long latency periods from exposure and the ability to follow patients long-term will be limited by duration of enrollment in the database.

- Calculation of HRT treatment duration and time since last exposure are based upon assumptions about actual use patterns because drug dispensing is all that can be directly observed using the HIRD.
- The study size is dependent on the rate of uptake of *Duavee* in the US. The study size projections are intentionally conservative (i.e., they are lower than Pfizer marketing forecasts of uptake in the US); to allow for adequate precision even if there is limited uptake in the first year following launch. Uptake will be evaluated at the end of Year 1 and, if needed, additional data sources or extension of study duration will be discussed in the 1st Interim Report.

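### The single index date in Section 7.4 closes the prior-E+P Duavee sub-analysis to new Duavee women after study year 1 at the latest

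*Protocol*

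**What the plan says.** Section 7.4 assigns each patient an "index date corresponding to the date of their first prescription for *Duavee* or E+P HRT treatment after 01 May 2014". Baseline is the period before that date. Section 7.2.1 leaves its length open ("e.g., 6 or 12 months to be determined by a priori analyses"), while the limitations in Section 7.9 already assume 12 months ("women who have had a hysterectomy before their baseline 12 month period").

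Section 7.1 starts follow-up at the first use of either treatment and lists "Switch from *Duavee* to an E+P HRT medication or vice-versa" among the censoring events. It mentions no second index date and no second cohort membership.

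Against this, the Abstract says that patients with prior E+P use in either cohort "will be excluded from the main analyses, but will be included in sub analyses". Sections 7.1, 7.2.1 and 7.2.2 repeat the plan, and Section 7.7.6.1 lists prior-E+P users of both treatments as a group to be described. Section 7.7.2 defines the group as "Women with a previous history of E+P HRT use, different from their index drug" and limits its analysis to incidence rates with confidence intervals. Section 7.1 also says that new users of both treatments will be identified in each of the four study years, and sets the calendar: "Study years and reporting intervals will run from May 1 through April 30 of the next year".

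**The concern.** The sub-analysis needs women whose index drug is Duavee and who filled E+P during baseline. Under the index rule, an E+P fill after 1 May 2014 cannot sit in a Duavee baseline, because it is the index fill of an E+P cohort member. When she later starts Duavee she is censored, not re-indexed. The women the sub-analysis is meant to describe are thus sent to the other cohort, unless they stopped E+P before launch and started Duavee soon after.

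At stake is what the second, third and final reports can say about women who move from E+P to Duavee. Those reports could extend follow-up of Duavee women who entered in the launch months, but could add no new ones. The launch months are also when Section 7.9 allows for limited uptake. The E+P side of the same sub-analysis is hit less hard at the start, because women already on E+P at launch refill shortly after 1 May 2014 and are indexed then.

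**Working it through.** The protocol gives no projected size for the prior-E+P Duavee group, so there is no figure to reproduce. The check is date logic.

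**Inputs**
- Index rule: first fill of either drug after 1 May 2014 (Section 7.4).
- Baseline length B: 6 or 12 months (Section 7.2.1).
- Accrual: May 2014 to May 2018, 48 months (Section 7.1).
- Study year 1: 1 May 2014 to 30 April 2015 (Section 7.1).
- Switch from E+P to Duavee: censored, no re-entry described (Section 7.1).

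**Conditions**

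Let s be the months from 1 May 2014 to the first Duavee fill, and g the months from the last E+P fill to that Duavee fill.

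1. E+P in baseline requires g ≤ B.
2. Duavee as index drug requires no E+P fill after 1 May 2014, so the last E+P fill lies at or before that date: s ≤ g.

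Together: s ≤ g ≤ B.

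**Latest possible entry**
- B = 6: s ≤ 6, about 1 November 2014.
- B = 12: s ≤ 12, about 1 May 2015, the boundary of study year 1. Whether that one day counts depends on how a fill dated exactly 1 May 2014 is treated.

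Study years 2 to 4 therefore contribute no Duavee entrants under either length.

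**Entry window as a share of accrual time**
- B = 6: 6/48 = 12.5%.
- B = 12: 12/48 = 25%.

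**Share of women kept (illustration only)**

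The protocol gives neither the gap g nor the accrual pattern in this group. If Duavee starts are assumed to be even over 48 months, the share kept is the mean of g divided by 48:

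| Assumed gap g | Share kept |
|---|---|
| 12 months for every woman (maximum, B = 12) | 12/48 = 25% |
| 6 months for every woman (maximum, B = 6) | 6/48 = 12.5% |
| Uniform over a 12-month baseline, mean 6 | 6/48 = 12.5% |
| Uniform over a 6-month baseline, mean 3 | 3/48 = 6.25% |
| 3 months for every woman | 3/48 = 6.3% |
| 1 month for every woman | 1/48 = 2.1% |

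A simulation of 400,000 women with uniform gaps gave 12.5% (B = 12) and 6.2% (B = 6), in agreement. Front-loaded uptake would raise these shares and slow early uptake would lower them.

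**Does another analysis recover these women?** Section 7.7.4 repeats the main analyses with person-time after a switch included. That keeps some post-switch time for women who began as new E+P initiators. It does not give them a Duavee index date or a baseline measured before Duavee, and it does not place them in the prior-E+P group.

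**The case against.** The strongest reply is that the index date may be meant per drug. Sections 7.2.1 and 7.2.2 provide for Duavee use in baseline, which the single-date rule makes all but impossible given a May 2014 launch. Section 7.7.2 speaks of prior use that differs from the index drug. Figure 4, which shows the flow into each analysis, was not available here. This is a fair reading of intent. It shows that the sections conflict, but the only stated rule is the one in Section 7.4, and no text describes a second index date.

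The protocol names 6 and 12 months as examples. A 24-month baseline would move the limit to about 30 April 2016, but nothing in the protocol proposes one.

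One entry per woman is also a legitimate choice for the main analysis. Section 7.7.2 explains why past HRT users are kept out of the new-user comparison. That stands, and it is why the change should be confined to the sub-analysis.

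Four stronger readings are tempting but not supported:

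- *Almost all such women are lost.* The documents fix the calendar window, not the share of women.
- *Their events after the switch are never counted.* Section 7.7.4 retains some post-switch time, although it does not say that this time is attributed to Duavee.
- *The sub-analysis cannot reach its four-event threshold.* In the prior-E+P sub-analysis that threshold governs only the stratified rates. Follow-up continues after discontinuation (Section 7.1), so the 10-month treatment duration under Table 1 is not the time at risk. The pilot E+P cohort averaged 89,438/50,350 = 1.78 person-years per woman. The number of prior-E+P Duavee women is not given, so no event count can be defended.
- *These women are the closest US counterpart of the EU population "for whom treatment with progestin-containing therapy is not appropriate".* Section 5 says only that the broader US indication should cover that population; it does not identify it with prior E+P users.

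**Conclusion.** The point holds as a conflict between the index rule and the planned sub-analysis. Read as written, Sections 7.4 and 7.1 stop Duavee entry with E+P in baseline at about 1 November 2014 (6-month baseline) or 1 May 2015 (12-month baseline). The window is at most 12.5% or 25% of the accrual period, with no Duavee entrants in study years 2 to 4. This rests only on the stated index rule, the absence of re-entry, and a baseline of 12 months or less. The proportion of women lost remains unknown.

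The affected analysis is secondary and limited to incidence rates, and the primary comparison of new initiators does not depend on it. It should be fixed, preferably before the analytic dataset is extracted, but it is not a fatal flaw.

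**What to change.** In Section 7.4, add a rule for the prior-E+P sub-analysis only: the Duavee index date is the first Duavee dispensing on or after 1 May 2014, regardless of earlier E+P fills, and baseline is assessed before that date. Keep one entry per woman in the main new-user analysis.

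Then bring the other sections into line:
- Section 7.1: state that censoring an E+P woman at a switch ends her E+P follow-up but does not bar entry to the Duavee sub-analysis.
- Sections 7.2.1, 7.2.2 and 7.7.2: use one definition of prior E+P use. State whether a woman refilling the same E+P product belongs to the sub-analysis, since only Section 7.7.2 requires the earlier product to differ from the index drug.

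The cost is a few sentences and some cohort programming on data already in the database. The small downside is that some women will contribute E+P time and later appear in the Duavee sub-analysis. That matters little where only incidence rates are estimated, and the reports can state how many women this concerns.

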7.3. Variables and Measurement

7.3.1. Exposure

The analyses will identify exposure to *Duavee* or E+P HRT treatment based on pharmacy claims with applicable Generic Product Identifier (GPI) codes. A list of included products and the GPI codes is provided in Appendix 2.

E+P HRT comparator products were chosen and must have been commercially available in the US with an indication for the treatment of moderate to severe VMS associated with menopause or the prevention of postmenopausal osteoporosis.

The analyses will define exposure to *Duavee* or E+P HRT as follows: Patients will be categorized as having “current use” for *Duavee* or E+P HRT from their index date through to 30 days after the date when the supply of their last consecutive prescription is calculated to have been used. Prescriptions will be defined as consecutive if not more than 30 days has passed between the days supply of two adjacent prescriptions. Otherwise, a new treatment segment will be defined. The 30-day grace periods allow for the possibilities of intermittent inconsistent use and saving of dispensed pills, by which a patient may still be taking the medication even after exhausting the available supply from their most recent dispensing. For each patient, duration of exposure will be based upon the summation of recorded supply (in days) across all of their study treatment segments. Multiple treatment segments due to intermittent HRT use will be summed when calculating duration of exposure. The study will measure each exposure segment that occurs during the follow-up period in order to support analyses that consider duration of exposure and time since most recent exposure (defined as time from date of treatment end to censoring). Patients with long periods of follow-up that contain multiple treatment segments will be reflected in the variables of duration of exposure and time since most recent exposure.

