7.3.4. Covariates

The study will identify and describe the following variables prior to initiation of *Duavee* or comparator E+P HRT treatment. Applicable operational definitions, including International Classification of Diseases, 9th Revision, Clinical Modification (ICD-9-CM) diagnosis, ICD-9-CM procedure, Current Procedural Terminology (CPT) and Healthcare Common

Procedure Coding System (HCPCS) codes used to identify each variable are shown in Appendix 2.

Patient characteristics:

- Age;
- US region of residence;
- Year of cohort entry (ie, index date); and
- Duration of health plan eligibility prior to cohort entry (in months)

Medical conditions diagnosed during the baseline period:

- Vasomotor symptoms;
- Obesity;
- Osteoporosis;
- Cerebrovascular disease;
- Hyperlipidemia;
- Hypertension;
- Breast pain
- Benign breast lumps (fibrocystic nodule)
- Diabetes;
- Renal disease;
- Osteoarthritis;
- Major depression;
- History of CHD
- History of gallbladder disease;
- History of thyroid disease;
- Family history of cancer;

- At least one diagnosis code indicative of a prior safety event of interest (exclusive of cancers as this is a baseline exclusion criterion).

Use of prescription medications during the baseline period prior to the start of *Duavee* or E+P HRT:

- Corticosteroids;
- Lipid lowering agents;
- Antihypertensives;
- Antidepressants;
- Sedatives/hypnotics;
- Anticonvulsants;
- Antimycobacterials;
- Macrolides;
- Antifungals;
- Antivirals;
- Antidiabetics;
- History of oral contraceptive use;
- History of intrauterine device (IUD) exposure; and
- Unopposed estrogen HRT
- Selective estrogen receptor modulators (SERMs)
- Testosterone
- Local hormone treatments

Additionally, the analyses will describe the most frequently occurring diagnoses and medications seen during the baseline period, the reasons that follow-up was censored and characteristics of medication use during the follow-up period, specifically duration of therapy and time since most recent exposure (measured at the time of censoring from study).

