7.7.1. Main Analyses

The analyses will describe patients that initiate *Duavee* and the comparator E+P HRT cohort with respect to demographic and clinical characteristics as enumerated in [Section 7.3.4](#). Reasons for censoring will also be described by exposure group. Descriptive comparisons of the two cohorts will be done to document their differences at baseline and to identify potential confounders to be addressed in the propensity matching.

For each of the primary endpoints (i.e., endometrial hyperplasia and endometrial cancer), an IR will be calculated as the number of women meeting a claims-based algorithm for each outcome (first event only) divided by person-time at risk.

The IR and its associated 95% CI will be presented for each cohort overall and stratified by categorical patient age at cohort entry, total duration of *Duavee* or E+P HRT treatment (long vs. short), time since last exposure to *Duavee* or E+P HRT, exposure to local hormone therapy (See Appendix 2), and by presence (Y/N) of an osteoporosis diagnosis within the 90 days before or after initiation of *Duavee* or E+P HRT. Duration of treatment and time since last exposure will be categorized based on observed data distributions. The feasibility of these stratifications and of a possible analysis that stratifies simultaneously by duration of treatment and time since last exposure will be determined based on the number of observed safety events.

Further details of the validation process are described in Appendix 3 and will be contained in the separate Endpoint Algorithm Development Report.

Hazard ratios will be estimated that represent the relative risk associated with initiating *Duavee* as compared to E+P HRT. It is planned to conduct both crude (unadjusted) and adjusted analyses to assess the HR for each of the primary endpoints. Adjusted analyses will use propensity score matching to ensure comparability between treatment groups. Further discussion of the methods to be used in computing propensity scores is included in [Section 7.7.3](#).

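### Covariates and the cancer exclusion stop before the fill date while follow-up starts on it, so diagnoses first coded on that day are lost as baseline data and prevalent disease can pass as incident

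*Protocol*

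**What the plan says.** **Index date.** Section 7.4: "Each patient will have an index date corresponding to the date of their first prescription for" Duavee or E+P HRT. Section 7.3.1 identifies exposure "based on pharmacy claims with applicable Generic Product Identifier (GPI) codes", so this is a dispensing date.

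**Baseline.** Section 7.4: "Baseline characteristics will be assessed from patient data collected prior to their index date (baseline period". Section 7.3.4 repeats the timing: "The study will identify and describe the following variables prior to initiation of" the study drug, with comorbidities listed under "Medical conditions diagnosed during the baseline period". That list includes vasomotor symptoms, obesity, osteoporosis and prior non-cancer safety events. The cancer exclusion in Section 7.2.2 is likewise limited to the baseline period.

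**Follow-up.** Section 7.1: "Follow-up will continue from the first use of" either treatment. Section 7.3.1 counts current use "from their index date through to 30 days after the date when the supply of their last consecutive prescription" runs out. Section 7.7.5 states that there is no discrete risk window.

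**What spans the index date.** The osteoporosis stratum in Section 7.7.1 uses an "osteoporosis diagnosis within the 90 days before or after initiation of" treatment. It stratifies incidence rates and is not the propensity score covariate of Section 7.3.4. The hysterectomy rule in Section 7.1 also reaches into follow-up. No comparable rule covers other diagnoses dated on the index day.

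**The concern.** In claims data, the visit that leads to a prescription and the fill of that prescription can carry the same date. Under the stated windows, whatever is coded at that visit then lies outside baseline and inside follow-up. Two things follow.

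- **Covariates.** Conditions recorded because treatment is being started, or reviewed at that visit, do not reach the propensity score unless they were also coded earlier. Obesity matters in particular: Section 7.9 says body mass index is not available, so a lost obesity code has little to replace it.
- **Endpoints.** A cancer first coded on the fill day does not exclude the woman. A hyperplasia first coded that day is not recorded as history. In both cases disease that was present before any drug effect was possible may later be counted as a new event.

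At stake are how well the matching captures confounders and whether incident events on the two primary endpoints are separated from prevalent disease.

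**Working it through.** **1. Where an index-day code falls.** The plan has no figure of its own on this point, so the first step is a reading of the text.

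| Item | Window in the protocol | Index-day code |
|---|---|---|
| Diagnosis covariates (7.3.4, 7.4) | before the index date | not counted |
| Cancer exclusion (7.2.2) | baseline period | does not exclude |
| Prior hyperplasia (7.3.4) | baseline covariate, not an exclusion | not recorded as prior |
| Follow-up (7.1) | from first use | inside |
| Current use (7.3.1) | from the index date | inside |

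**2. When a diagnosis is actually lost.** Both conditions must hold: the fill is on the day of the visit, and the condition was not coded earlier in baseline.

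**3. When an index-day code can become an event.** Appendix 2 asks for two outpatient codes or one inpatient code for breast, ovarian, renal, gastrointestinal and all cancers and for renal adenoma. An index-day outpatient code can therefore be the first of the two. VTE, MI and stroke/TIA need a hospitalization, and thyroid cancer needs a thyroidectomy plus at least two codes. The algorithms for endometrial cancer and hyperplasia are not yet fixed.

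**4. How many Duavee events are expected in year 1.** Inputs from Table 1 (Section 7.5): 1,800 Duavee users and 10 months of person-time each; 27,768 E+P person-years with 129 hyperplasia events and 29 endometrial cancers; stated upper limits at a true HR of 1.0 of 2.26 and 5.60.

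- Person-years: 1,800 × 10/12 = 1,500.
- Hyperplasia: 1,500 × 129/27,768 = 6.97. Endometrial cancer: 1,500 × 29/27,768 = 1.57.
- Check against the plan, upper limit = exp(1.96 × √(1/E₁ + 1/E₀)), where E₁ and E₀ are the Duavee and E+P event counts: 2.14 for hyperplasia and 4.99 for cancer, against 2.26 and 5.60. The stated limits therefore imply slightly fewer Duavee events.
- Solving for those, E₁ = 1/[(ln U/1.96)² − 1/E₀], where U is the stated upper limit: hyperplasia 1/(0.1731 − 0.0078) = 6.05; cancer 1/(0.7726 − 0.0345) = 1.35.

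One misassigned case adds 1/6.97 = 14% to 1/6.05 = 17% to the hyperplasia count, and 1/1.57 = 64% to 1/1.35 = 74% to the cancer count. Section 7.7.6.2 allows an HR once each cohort has one event and there are four in total, so a single prevalent case could be the one that meets the Duavee requirement.

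**5. What uncaptured confounding could do.** The documents give no prevalences or risk ratios, so these are assumptions. For a binary factor left uncaptured in proportions p₁ and p₀ of the two cohorts, the bias factor is (1 + p₁(RR − 1))/(1 + p₀(RR − 1)).

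- 10% in both cohorts: 1.00 for any RR.
- 10% against 8%, RR 1.5: 1.05/1.04 = 1.01.
- 20% against 10%, RR 3: 1.40/1.20 = 1.17.

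Equal fill delays do not by themselves remove the problem. Assume true prevalences of 60% and 40%, with 64% captured in each cohort. Among women recorded as negative, the condition is present in 0.216/0.616 = 35% and 0.144/0.744 = 19%. With RR 1.5 to 2 the bias factor in that stratum is about 1.07 to 1.13.

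**The case against.** **Ending the window before exposure is a recognised choice.** It keeps post-exposure information out of the covariates. That stands, and there is no contradiction in the text. But a diagnosis made at the prescribing visit can hardly be an effect of a drug dispensed that day. The window is also fixed in the protocol, so this is not a detail left open for the analysis plan.

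**Much will be captured anyway.** Most listed comorbidities are chronic and will often have an earlier code in baseline. That stands and limits the loss.

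**A reader might infer that the indication steers women to one product and so confounds the comparison.** The documents do not support this. Section 5 gives Duavee the two US indications, and Section 7.3.1 requires the E+P comparators to have one or the other of them. Nothing says that vasomotor symptoms or osteoporosis drive the choice, or that vasomotor symptoms raise the risk of any endpoint. The two-sided osteoporosis window comes without a reason, so it does not show that the protocol expects codes to cluster at initiation.

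**A reader might also infer a large spurious imbalance.** Suppose true prevalence of vasomotor symptoms is 60% in both cohorts, 50 to 70% of these women are coded only at the prescribing visit, and same-day fills are 60% for E+P and 30% for Duavee. Recorded prevalence, 0.60 × (1 − share coded only then × same-day share), is then 42% to 35% against 51% to 47%, a gap of 9 to 13 points. The gap comes entirely from the assumed difference in fill delay, which nothing in the documents suggests. With equal delays it vanishes. It is also a gap in a covariate and not an effect on the HR; with equal true prevalence there is no real imbalance to leave behind.

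**Nor does any endpoint code at the visit count as an event.** One outpatient code meets none of the secondary algorithms in Appendix 2, and the primary ones are undetermined. What remains is that an index-day code can contribute to an event completed later.

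**Conclusion.** The point holds as a modest flaw in a stated rule. Codes dated on the index day are outside baseline and inside follow-up. Diagnoses first recorded then are lost from the propensity score, and cancer or hyperplasia first recorded then is not set aside as prevalent.

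Its size cannot be derived from the documents. Bias in the HR requires that the uncaptured factors are related to endpoint risk and differ between cohorts, or that index-day prevalent codes differ between cohorts. The bias factors of 1.00 to 1.17 illustrate assumed inputs and are not estimates. The firmer argument is the thin Duavee event count: at about 6 to 7 hyperplasia events and 1 to 2 endometrial cancers in year 1, one prevalent case counted as incident would visibly move the rate. That in turn assumes that the final primary algorithms would accept such a case. It is worth correcting because the correction costs so little.

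**What to change.** - **Sections 7.2.2, 7.3.4 and 7.4:** assess diagnosis and procedure covariates, and the diagnosis-based exclusions, up to and including the index date. Keep drug-use covariates and the new-initiator washout strictly before it. The separate hysterectomy rule in Section 7.1 can stay.
- **Section 7.1:** start events and person-time on the day after the index date.
- **Section 7.1, prevalent disease:** treat a woman with an endpoint code on or before the index date as prevalent for that endpoint, so that repeat coding soon afterwards is not counted as incident. The later start alone does not achieve this for hyperplasia, because prior hyperplasia is not an exclusion: a woman coded on the index day would stay at risk, and her next claim could count.

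**Cost:** a few sentences, with no new data. The few events first coded on the index day are dropped, and these can hardly be effects of a drug dispensed that day. Women with an earlier code for a non-cancer endpoint, whom Section 7.3.4 now handles only through a covariate, would leave the analysis of that endpoint; the reports should give their number by cohort.
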